4.4 Safety Objectives

The study aims to validate the overall implementation of the new feedback system by testing for unexpected behaviour from the IMD and to identify any new risk factors to ensure the safety of the devices before they are released to the market.

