6.2 Methods of minimising bias

6.2.1 Randomisation

A single group assignment to the IMD will be used for the field trial. All subjects will wear the RMD for the first field test period and then the IMD for the second field test period. This procedure will be followed for all three phases. The lab tests, which include the live feedback test and the speech test, conducted in the clinic will be randomised. The live feedback and speech test order will be randomised based on a list created by the statistician. This means that for the live feedback and speech tests the subjects will be randomised by the hearing aid condition. This reduces bias by using a different starting and ending condition as the last condition has a higher chance of scoring higher due to a learning effect from the speech test. Additionally, the speech lists used for the speech test will be randomised as each list presents the same words but in different orders. The randomisation list will not be concealed from the PI but should be in the ISF so that the PI knows in which condition order to test each subject.

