8. STUDY INTERVENTION

8.1 Identity of Investigational Products (medical device)

For all three phases the treatment will be approximately 10 days of use with the IMD during which they will not use the RMD. They will be fit with the RMD for the first 10 +/- 5 days field test and then switch to the IMD for the assigned period of 10 +/- 5 days.

There will be lab tests during which the participants will use the RMD and the IMD, for up to 1.5 hours at a time during testing in the clinic.

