9.2.3.1 Adverse events

For the recording of adverse events the subjects will be asked for a description of the event including time/date of onset, how long it lasted, how many times it occurred, and if it caused discomfort or pain or a disruption of hearing ability. Before the end of each appointment, the subjects will be asked if they have experienced any adverse events. It will be explained that adverse events are not restricted to problems related to the hearing aids or their hearing but can include allergies, broken legs, headaches, etc. They will be recorded on the AE forms in the CRF.

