10.1 Medical Device Category C studies

Device deficiencies and all **adverse events (AE)** including all **serious adverse events (SAE)** are collected, fully investigated and documented in the source document and appropriate case report form (CRF) during the entire study period, i.e. from patient's informed consent until the last protocol-specific procedure, including a safety follow-up period [ISO 14155]. Documentation includes dates of event, treatment, resolution, assessment of seriousness and causal relationship to device and/or study procedure.

The information on AEs is systematically collected by the clinician at each study visit. They will follow the procedures outlined in SOP ID106_AE Reporting. The subjects are asked at each appointment if they have experienced any events since the last appointment. During the appointments the subjects are then asked questions about the event to gather details and to determine the severity of the event. If a subject reports pain that results in the inability to use the device, he will be withdrawn from the study in order to avoid any pain from using the device and to remove partial data from the study. For reports of pain caused by insertion or the dome itself, the problem can be addressed in the clinic. For example, a different style or size of dome can be placed on the hearing aid, and re-training of insertion can be performed with the subject to avoid wrong or forceful insertion of the device. For reported pain they will be advised to not wear the device for 24 hours before resuming use.

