10.1.1 Definition and Assessment of (Serious) Adverse Events and other safety related events

Adverse Event (AE)

Any untoward medical occurrence, unintended disease or injury or any untoward clinical signs (including an abnormal laboratory finding) in participants, users or other persons whether or not related to the investigational medical device [ISO 14155: 3.2].

This includes events related to the IMD or the RMD and to the procedures involved. For users or other persons this is restricted to events related to the investigational medical device.

Adverse Device Effect (ADE)

Adverse event related to the use of an investigational medical device [ISO 14155: 3.1].

This includes any adverse event resulting from insufficient or inadequate instructions for use, deployment, implantation, installation, operation, or any malfunction of the investigational medical device. This includes any event that is a result of a use error or intentional misuse.

AEs/ADEs include:

- Exacerbation of a pre-existing disease or condition.
- Increase in the frequency or intensity of a pre-existing episodic disease or medical condition.
- Any disease or medical condition detected or diagnosed after treatment with the study intervention device even though it may have been present yet undetected prior to the start of the clinical investigation.
- Any continuous persistent disease or symptoms present at baseline that worsen following the start of the clinical investigation.

- Events considered by the investigator to be related to any of the clinical investigation-mandated procedures.
- Abnormal assessments, e.g. physical examination findings, will be reported as AEs/ADEs if they represent a clinically significant finding that was not present at baseline or that has significantly worsened during the course of the clinical investigation.
- Test abnormalities will be reported as AEs/ADEs if they represent a clinically significant finding, symptomatic or not, which was not present at baseline or has significantly worsened during the course of the clinical investigation.

AEs/ADEs do not include:

- Pre-planned interventions or occurrences of endpoints specified in the CIP are not considered AEs/ADEs, if not defined otherwise.
- Unrelated medical or surgical procedures, e.g. surgery, endoscopy, tooth extraction, transfusion. However, the event leading to the procedure may be considered an AE. If this event is serious, the procedure will be described in the SAE/SADE narrative.

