11.4.5 Safety analysis

The adverse event risks of taking part in the study have been assessed to be low. Numbers of adverse events and serious adverse events will be cross-tabulated for each IMD style and categorised by severity. No formal statistical analysis will be conducted, but AEs and SAEs will be closely monitored throughout the process.

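### The adverse event table is laid out by IMD style and severity only, so it does not separate events that start on the marketed device from events that start on the new one

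*Protocol*

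**What the plan says.** Section 11.4.5 (Safety analysis) gives the layout of the safety table: numbers of AEs and SAEs, "cross-tabulated for each IMD style and categorised by severity". It adds that "No formal statistical analysis will be conducted". It names no RMD column, no split by field-test period and no rule for assigning an event to a device.

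The surrounding sections set what enters that table:

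- **Order of devices (section 6.2.1):** "All subjects will wear the RMD for the first field test period and then the IMD for the second field test period". This applies to all three phases.
- **Length of wear (section 8.1):** participants have the RMD for a first field test of 10 +/- 5 days and then "switch to the IMD for the assigned period of 10 +/- 5 days".
- **Collection window (section 10.1):** AEs are collected from "informed consent until the last protocol-specific procedure", so the RMD period is covered.
- **Definition (section 10.1.1):** on the scope of AEs, "This includes events related to the IMD or the RMD and to the procedures involved".
- **Recording (section 9.2.3.1):** each event is described by "time/date of onset, how long it lasted, how many times it occurred", among other items. Section 10.1 adds the causal relationship to device or procedure.
- **Purpose (section 4.4):** the safety objective includes "to identify any new risk factors to ensure the safety of the devices" before market release.

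**The concern.** The study has a within-person design: each participant wears a marketed device and then the new one. The AE table uses only one device dimension, the IMD style, and that is the same thing as the phase. Events from two different devices can therefore end up in one cell that carries the name of the new device.

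Two errors are possible, in opposite directions. The count shown for an IMD style can be too high, because it includes events that started on the RMD. A real excess on the IMD can also be diluted, because it is averaged with RMD time. The reader of the report could see neither.

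This matters most where the hardware of the two devices differs. In Phase 2 the IMD is rechargeable and the comparator is not, since the synopsis says that no rechargeable device is marketed. Section 10.1 lists battery events among the foreseeable AEs. On the literal reading, a battery event on the comparator would appear in the row of the rechargeable IMD. In Phase 3 the comparator is a separate marketed product.

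**Working it through.** Section 11.4.5 states no figure, so there is none to reproduce, and the sample size in section 11.2 is not affected. The check compares the stated layout with the exposure that the design creates.

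**1. Exposure.** Inputs: 22, 22 and 11 participants in Phases 1, 2 and 3 (section 6.1); nominally 10 days on each device (section 8.1).

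| Phase | RMD participant-days | IMD participant-days | Pooled under the IMD style |
|---|---|---|---|
| 1 | 22 × 10 = 220 | 220 | 440 |
| 2 | 22 × 10 = 220 | 220 | 440 |
| 3 | 11 × 10 = 110 | 110 | 220 |
| All | 550 | 550 | 1,100 |

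**2. RMD share of field-test time.** Share = RMD days / (RMD days + IMD days).

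- Nominal: 10 / (10 + 10) = 50%.
- Shortest RMD period with longest IMD period: 5 / (5 + 15) = 25%.
- Longest RMD period with shortest IMD period: 15 / (15 + 5) = 75%.

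**3. What pooling does to the event count.** The protocol gives no AE rates, so this step is an illustration. Assume equal exposure, and let r be the ratio of the IMD event rate to the RMD event rate. The share of tabulated events that started on the RMD is 1 / (1 + r). The pooled rate relative to the RMD rate is (1 + r) / 2.

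| r (assumed) | Share of events from the RMD period | Pooled rate / RMD rate |
|---|---|---|
| 1 | 50% | 1.0 |
| 1.5 | 40% | 1.25 |
| 2 | 33% | 1.5 |
| 3 | 25% | 2.0 |

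If the rates are equal, half the events in a cell come from the RMD, and the cell holds twice the IMD-period count. If the IMD truly doubles the rate, the pooled rate is only 1.5 times that of the RMD.

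**4. The two readings of section 11.4.5.**

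- *All AEs are counted.* Section 11.4.5 does not restrict its counts to the IMD period, and section 10.1.1 includes RMD events. The cell then mixes both devices, as in steps 2 and 3.
- *RMD-period events are left out.* The cell is then clean, but nothing stands beside it for comparison.

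Neither reading yields a table that shows whether the IMD adds events.

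**5. Whether the data allow a split.** They do. Onset date and time are recorded, and the switch from RMD to IMD takes place at a dated visit (Visit 2). The exception is the lab sessions: both devices are worn at the feedback test (Visit 2) and at the speech test (Visit 3), so an event that starts there may not belong to one device.

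**The case against.** The strongest defence has five parts.

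- **Table layout belongs in the statistical plan.** Appendix 6 is a statistical plan and is not shown. Columns, denominators and onset rules are commonly settled there. This would answer a complaint that detail is missing. It does not fully answer this point, because the protocol itself fixes a grouping, and that grouping does not fit its own design.
- **No attribution rule is stated.** A reader might infer that the plan orders RMD-period events to be counted under the IMD. The text does not say so. That is the literal reading of sections 11.4.5 and 10.1.1 together, but omission or a separate display is also possible. This objection stands, and the point is worded accordingly.
- **The devices can still be compared.** A reader might infer that no safety comparison is possible. That is wrong. Onset and causality are recorded, and the safety items of the product questionnaire (section 5.3) are answered once per device, with the answers compared (section 5.2). This stands in full. Those items concern unexpected noise and device behaviour, however, and do not replace the AE and SAE table. Relatedness is only a partial substitute: section 11.4.5 does not tabulate it, and the graded scale in section 10.1.1 is headed for SAEs and mostly worded for the investigational device.
- **Few events are expected and no test depends on the table.** Section 10.1 calls the foreseeable events improbable, and the analysis is descriptive. This limits the consequence. With few events, though, placing a single one under the wrong device weighs more.
- **A split would not be a fair comparison.** The RMD always comes first, so device and period are confounded, and the RMD is not a concurrent reference. Events can also persist from one period into the next. This stands. It limits what a split table can prove, but it is no reason to merge the periods.

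**Conclusion.** The point holds as a mismatch between the stated table and the within-person design. The planned AE and SAE table does not separate new-device from marketed-device events, whichever way RMD-period events are handled, and so it does not serve the objective in section 4.4.

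The size that the documents support is the share of exposure: nominally 50% of field-test wear is on the RMD, and 25% to 75% at the extremes of the windows. A reader might go further and say that half of the tabulated events would come from the RMD. That needs equal event rates on both devices and the literal reading of section 11.4.5; the protocol gives no rates and no explicit assignment rule.

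The change is worth making before the analysis, because the study is a pre-market safety validation. It concerns descriptive reporting only and leaves the primary analysis and the sample size untouched.

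**What to change.** Amend section 11.4.5, or settle it in the statistical plan with a reference from the protocol, as follows:

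1. Within each phase, tabulate AEs, SAEs and device deficiencies by the device worn at onset: RMD period or IMD period. List separately the events that start in a lab session where both devices are worn.
2. Show severity and relatedness, with relatedness stated for the RMD as well as the IMD.
3. Give the number of participants and the days of wear on each device as denominators.
4. State that the comparison is descriptive, because device order is fixed and device is confounded with period.

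The cost is an extra column or two in one table and a few sentences of text. Onset dates are already recorded on the AE forms, and days of wear follow from the visit dates. No new data, visits or participants are needed.

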11.4.6 Deviation(s) from the original statistical plan

Due to the home-based nature of the trial, it is possible that there will be a few deviations from the study protocol, e.g. not wearing hearing aid, manipulation issues, misplacement, etc.

As well as non-compliance with the protocol, there could be other protocol deviations, for example if follow-up assessments took place outside the pre-specified ± 10 days window. The numbers and proportions of participants with protocol deviations will be summarised with details of type of deviation provided. No formal statistical testing will be undertaken.

11.5 Handling of missing data and drop-outs

Unless specified otherwise in each objective, no statistical techniques will be used to impute missing data. If a subject's data are missing for any reason, that subject will not be included in that portion of the analysis. The number of subjects included in each analysis will be reported so that the potential impact of missing data can be assessed.

12. QUALITY ASSURANCE AND CONTROL

The Sponsor is responsible for implementing and maintaining quality assurance and quality control systems with written SOPs and Working Instructions. The PI is responsible for proper training of all involved study personnel.

12.1 Data handling and record keeping / archiving

Data will be archived with an electronic data management system. The subjects will be given numbers to maintain anonymity. There are also hard copies of subjects' charts that are kept in a locked file cabinet inside of the clinic room. Only the PI, statistician, Monitor, and Auditor will have access to the information. The information will always be archived under the identification number with a key to the identification codes stored in another location (described in chapter 2.8).

12.1.1 Case Report Forms

Participant identities are coded using a participant identification number.

The PI will enter protocol defined data into a web based Electronic Case Report Forms using an EDC-software that conforms to 21 CFR Part 11 (FDA guidance) requirements. Site staff will be given access to the EDC system after a training. The data are checked automatically for plausibility and discrepancies. The generated appropriate error messages, allow the data to be confirmed or corrected before being saved in the database. At the end of the study, the PI must certify that the data entered into the Electronic Case Report Forms are complete and accurate. After database lock, the PI will receive a CD-ROM of the patient data for archiving at the site.

The CRF contains the following information:

Field	Author
Date of examination	PI
Subject birth year	PI
Participant identification number	PI
Age	PI
Sex	PI
Otoscopy	PI
Standard audiometry	PI
Hearing loss classification	PI
Eligibility	PI
Trial information provided	PI
Date of Informed Consent	PI
Inclusion / Exclusion Criteria	PI
Ear disease	PI
Control hearing device serial numbers	PI
Real ear measure	PI
Investigational device serial numbers	PI
Results from WaKo	PI
Questionnaires received	PI
Questionnaires returned	PI

Devices returned	PI
IFU received	PI
Results from preference questionnaire	PI
Results from product questionnaire	PI
Results from SSQ questionnaire	PI
AEs / SAEs, ADE / SADE	PI
Next appointment	PI
Name, date, signature of PI	PI

12.1.2 Specification of source documents

The Principle Investigator will maintain adequate and accurate records to enable the conduction of the study to be fully documented and the study data to be subsequently verified. These documents will be classified into two different categories: PI's file, and subject clinical source documents. There will be a PI file or Investigator Site File (ISF) as well as corresponding subject files with source documents.

The PI's file will contain the CIP/amendments, IB/Instructions for use, CRFs, site standard operation procedures (SOPs) or reference to it, EC and CA approval with correspondence, informed consent, device records, staff curriculum vitae and authorization forms, screening and enrolment logs, site-specific subject identification code logs, and other appropriate documents/ correspondence as required by EN ISO 14155 and local regulations.

Subject clinical source documents include, but are not limited to subject hospital/clinic records, physician's and nurse's notes, appointment book, hearing test results, questionnaires, consultant letters, visit dates, signed Informed Consent Forms, randomisation numbers, SAEs, AEs, etc.

These two categories of documents must be kept on file by the PI for 10 years. If source documents are not durable as long as needed they must be preserved as a copy. When source documents are required for the continued care of the subject, appropriate copies should be made for storing outside of the site. The information will always be archived under the identification number with a key to the identification codes stored in another location (described in chapter 2.8).

For each subject enrolled an encoded electronic CRF must be completed and e-signed by the PI. This also applies to those subjects who fail to complete the study. If a subject withdraws from the study, the reason must be noted on the CRF.

Case report forms are to be completed immediately after the visit.

Source data corrections will only be performed by study site staff, authorized by the PI. All forms should be completed using a blue permanent pen and must be legible. Errors should be crossed out but not obliterated, the correction inserted, and the change initialled and dated by the PI, co-PI or other investigator.

The entries will be checked by the Monitor and any errors or inconsistencies will be checked immediately. The Sponsor will collect original completed eCRFs on a CD-ROM at the end of the study. The CD-ROM with the completed and e-signed CRFs will remain on site and archived.

Source data must be available at the site to document the existence of the study participants. Source data must include the original documents relating to the study, as well as the medical treatment and medical history of the participant.

12.1.3 Record keeping / archiving

(ICH/E6 6.13)

ICH: Data Handling and Record Keeping

All study data must be archived for a minimum of 10 years after study termination or premature termination of the clinical trial.

Trial documentation is stored in water and fire resistant locked boxes in the basement of the Sponsor's building,

12.2 Data management

12.2.1 Data Management System

The CRFs in this trial are implemented electronically using a dedicated electronic data capturing (EDC) system. The EDC system is activated for the trial only after successfully passing a test procedure.

All data entered in the CRFs are stored on a Windows server in a dedicated database located in Denmark.

12.2.2 Data security, access and back-up

The server hosting the EDC system and the database is kept in a locked server-room in Denmark. Only the system administrators have direct access to the server. A role concept with personal passwords (site investigator, statistician, monitor, administrator etc.) regulates permission for each user to use the system and database as he/she requires.

All data entered into the CRFs are transferred to the database using Secure Sockets Layer (SSL) encryption. Each data point has attributes attached to it identifying the user who entered it with the exact time and date. Retrospective alterations of data in the database are recorded in an audit table. Time, table, data field, original value and altered value, and the person are recorded (audit trail).

A multi-level back-up system is implemented. Back-ups of the whole system including the database are run several times per day. The back-up-data are stored in a secure place on a different storage-server.

12.2.3 Analysis and archiving

At final analysis, data files will be extracted from the database into statistical packages to be analysed. The database will be locked at this time, recorded in special archiving format and securely stored for at least 1 year. In addition, the PI will receive a CD-ROM of the trial data for archiving at the site.

12.2.4 Electronic and central data validation

Data can be entered into the database only after a check of completeness and plausibility. Furthermore, selected data points are cross-checked for plausibility with previously entered data for that participant.

Monitoring is used to validate entries with source data.

